6.2.3 Follow up period and trial completion

- Visit 7/End of Treatment (EOT) or when the patient is discontinued
- Adverse events and concomitant therapy assessment since last visit

- Review pulmonary rehabilitation attendance with patient and record information from pulmonary rehabilitation reports into eCRF for patients in the PR treatment group (for patients discontinued during first 12 weeks)
- Physical examination including vital signs
- SGRQ, KBILD and UCSD SOBQ
- Collect and download/review PROActive Tool from eDiary and activity monitor data
- Resting SpO₂
- Resting 12-lead electrocardiogram
- Blood samples for laboratory tests
- Urinary pregnancy test (done locally)
- Pulmonary function test including FVC
- DL_{CO}
- Six minute walk test
- 
- End Of Treatment page to be completed

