3.3.4 Withdrawal of patients from therapy or assessments

Patients may potentially be withdrawn from trial treatment or from the trial as a whole ("withdrawal of consent") with very different implications, please see [sections 3.3.4.1](#) and [3.3.4.2](#) below.

Every effort should be made to keep the randomised patients in the trial: if possible on treatment, or at least to collect important trial data.

Measures to control the withdrawal rate include careful patient selection, appropriate explanation of the trial requirements and procedures prior to randomization, as well as the explanation of the consequences of withdrawal.

The decision to withdraw from trial treatment or from the whole trial as well as the reason must be documented in the patient files and CRF (case record form).

In the event a patient or partner of a patient has become pregnant prior to withdrawal from the trial, the procedures in [Section 5.2.6.1](#) should be followed. If a patient becomes pregnant during the trial, the prescribing physician should be notified and continuation of nintedanib treatment addressed by the prescribing physician. Continued participation in the trial should be discussed with the clinical monitor.

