3.3.4.1 Withdrawal from trial treatment

An individual patient is to be withdrawn from trial treatment if:

- The patient wants to withdraw from trial treatment, without the need to justify the decision.
- The patient needs to take concomitant treatments that interfere with the required OFEV treatment.
- The patient can no longer be treated with trial procedures for other medical reasons (such as surgery, adverse events, other diseases, or pregnancy).
- The patient has repeatedly shown to be non-compliant with important trial procedures and, in the opinion of both, the investigator and sponsor representative, is not willing or able to comply with the trial requirements in the future.

Given the patient's agreement, the patient will undergo the procedures for early treatment discontinuation and follow up as outlined in the [Flow Chart](#) (FC) and [section 6.2.3](#).

For all patients the reason for withdrawal from trial treatment (e.g. adverse events) must be recorded in the CRF. These data will be included in the trial database and reported.

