3.3.4.2 Withdrawal of consent for trial participation

Patients may withdraw their consent for trial participation at any time without the need to justify the decision.

This will however mean that no further information may be collected for the purpose of the trial and negative implications for the scientific value may be the consequence. Furthermore it may mean that further patient follow up on safety cannot occur.

If a patient wants to withdraw consent, the investigator should explain the difference between treatment withdrawal and withdrawal of consent for trial participation and explain the options for continued follow up after withdrawal from trial treatment, please see [section 3.3.4.1](#) above.

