4.2.1.2 Management of other adverse events

Adverse events related to the study procedures such as pulmonary rehabilitation, 6MWT [REDACTED] as well as unrelated adverse events, will be managed as clinically indicated. If a patient experiences an adverse event which impacts their ability to continue with pulmonary rehabilitation (if assigned) or ability to continue with the exercise testing, the clinical monitor should be consulted regarding continued participation in the trial prior to discontinuation.

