6. INVESTIGATIONAL PLAN

6.1 VISIT SCHEDULE

This trial consists of two parts, a screening and an interventional period. The screening period consists of the time between signing consent and randomization, and will last a minimum of 7 days. The interventional period consists of the time from randomization through the week 24 assessment visit.

There are two screening visits (Visit 1, which must be preceded by a separate informed consent Visit 0) and 6 visits (Visits 2 to 7) planned within the 24 week interventional period. There is no follow up period in this trial.

After giving his/her informed consent, the patient will be screened for inclusion (see [Section 3.3.2](#) and exclusion criteria (see [Section 3.3.3](#)) for the trial at Visits 0, 1 and Visit 2 (refer to [Flowchart](#)).

The patient will be dispensed an activity monitor and ProActive tool (eDiary) at the consent visit, and will wear the activity monitor and use the eDiary for 7 days prior to Visit 1 for training purposes.

Visit 2 can be performed once the results from local laboratory of Visit 1 are obtained and the patient has worn the activity monitor and completed the eDiary for 7 days. If for any reason the screening phase for an individual patient lasts for more than 6 weeks, then the laboratory examination for Visit 1 has to be repeated before randomization. The patient will be randomized at Visit 2 if all inclusion and none of the exclusion criteria are fulfilled. Central HCRT is not required prior to randomization, but if historical HRCT is not available to be sent for central calculation of QLF, a scan should be obtained after screening/consent at the latest 7 days after Visit 2.

On treatment visits will be performed at 3, 6, 12, 18 and 24 weeks. Procedures for these visits are outlined in the flow chart and detailed instructions are available in [Section 5](#), select appendices and the ISF, as applicable.

Visit 7 is the end of treatment visit, there is no follow up period. Visit 7 procedures should be followed for early termination visits if possible.

If a patient misses a visit, the visit should be rescheduled as soon as possible. If unable to reschedule, the clinical monitor should be contacted.

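### No on-schedule week-12 or week-24 visit is specified for patients who stop trial treatment without withdrawing consent, although the protocol asks for their data

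*Protocol*

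**What the plan says.** Protocol, on stopping treatment:

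- Section 3.3.4 separates withdrawal from trial treatment from withdrawal from the trial. It asks that randomised patients be kept "if possible on treatment, or at least to collect important trial data".
- Section 3.3.4.2 tells the investigator to "explain the options for continued follow up after withdrawal from trial treatment", and refers back to 3.3.4.1.
- Section 3.3.4.1 says that, if the patient agrees, "the patient will undergo the procedures for early treatment discontinuation and follow up as outlined in the" Flow Chart and Section 6.2.3.
- Section 6.2.3 lists a single visit: "Visit 7/End of Treatment (EOT) or when the patient is discontinued". Its item on rehabilitation attendance is marked "for patients discontinued during first 12 weeks", so stops before the primary time point are foreseen.
- Section 6.1 states "Visit 7 is the end of treatment visit, there is no follow up period" and "Visit 7 procedures should be followed for early termination visits if possible". The Flow Chart ends at Visit 7, the only column in which participation is concluded.

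On analysis:

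- Protocol 7.3 bases efficacy on all randomised patients, and 7.3.1 uses complete cases for the primary endpoint. Section 7.3.2 plans a repeated-measures mixed model for week 24 and multiple imputation as a sensitivity analysis of the primary endpoint.
- SAP 6.6 uses observed cases without imputation. SAP 6.7 assigns 6MWT, spirometry and questionnaire values from days 2 to 126 to week 12, and from day 127 onwards to week 24.
- SAP 4 limits primary and secondary endpoints to descriptive measures after termination of the trial. The imputation text in SAP 6.6.1 and 7.4.2 is struck through.

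**The concern.** A comparison of all randomised patients needs outcomes at the planned times whether or not treatment continued. The protocol states that intention but attaches no visits to it. A site that follows the cross-references does one early Visit 7 and has no instruction to see the patient again at week 12 or week 24.

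Two results are at stake. One is the primary endpoint, the change in 6MWD at 12 weeks. The other is the main objective of an enduring effect, which rests on week 24, after rehabilitation has ended. If patients who stop differ from those who continue, summaries of observed values no longer describe the randomised groups.

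**Working it through.** **1. Following the cross-references.** Section 3.3.4.2 leads to 3.3.4.1, which leads to the Flow Chart and 6.2.3. Both end at Visit 7, and 6.1 excludes anything later. The follow-up that 3.3.4.1 mentions is not scheduled anywhere on this path.

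**2. What the analysis receives for 6MWD.** These rows apply the SAP 6.7 windows and its rule that the measurement nearest the planned day (day 85 for week 12) is used.

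| Case | Week-12 value | Week-24 value |
|---|---|---|
| Stop before Visit 5, no early visit attended | missing | missing |
| Stop before Visit 5, early walk between days 2 and 126 | the early walk, off schedule | missing |
| Visit 5 done, early Visit 7 by day 126 | the walk nearer day 85, normally Visit 5 | missing |
| Visit 5 done, early Visit 7 from day 127 | Visit 5 walk | the early walk, counted as week 24 |

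**3. The plan's own figures.** Protocol 7.7 gives a 30 m difference, SD 85 m, two-sided 0.05 and 80% power. The noncentral-t calculation gives 127 per arm, 254 in total (power 80.0%), as stated. With 10% dropout, 127 / 0.9 = 141.1, which the protocol states as 141 per arm (282); rounding up would give 142. The planned 145 per arm exceeds both. No stated figure is in dispute.

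**4. Bias where stoppers' values are missing.** Let s be the share of the rehabilitation arm that stops and has no value, and let G be the mean outcome of completers minus the mean that stoppers would have had. The mean over the whole arm is (1 − s) × completers + s × stoppers = completers − s × G. The observed-case mean is therefore too high by s × G. This takes loss in the control arm to be uninformative. The values of s and G are assumptions; the documents give only 10% dropout.

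| s | G = 30 m | G = 70 m |
|---|---|---|
| 10% | 0.10 × 30 = 3 m (10% of 30 m) | 0.10 × 70 = 7 m (23%) |
| 20% | 0.20 × 30 = 6 m (20%) | 0.20 × 70 = 14 m (47%) |

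**5. Bias where the early walk counts as week 12.** The formula in step 4 does not apply, because these patients are included. The error in the arm mean is s × (mean early walk − mean week-12 walk that would have been seen). The documents fix neither its size nor its sign. A walk taken during an adverse event could be worse than the later one; a walk taken before further disease progression could be better.

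**6. Power.** This uses the inputs of step 3 with 145 randomised per arm.

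| Loss, rehabilitation / control | Evaluable | Power |
|---|---|---|
| 0% / 0% | 145 / 145 | 85.0% |
| 10% / 10% | 130 / 130 | 80.9% |
| 20% / 10% | 116 / 130 | 78.6% |
| 30% / 10% | 101 / 130 | 75.5% |

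The power cost is modest, so bias is the larger issue.

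**The case against.** A reader might infer that everyone who stops rehabilitation leaves the trial, that their week-12 outcomes are lost, and that the loss falls on one arm and favours rehabilitation. The documents do not support that reading.

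- **Leaving is not automatic.** Section 3.3.4 distinguishes stopping treatment from leaving. For adverse events that affect rehabilitation, Section 4.2.1.2 says "the clinical monitor should be consulted regarding continued participation in the trial prior to discontinuation". Section 5.1.2.1 keeps patients who cannot complete the walk test after randomisation. SAP 6.2 records low rehabilitation attendance as a deviation without excluding anyone. The reference to early termination in 6.1 can also be read as covering only patients who leave the trial.
- **The week-12 value is not simply lost.** The early Visit 7 includes the 6MWT, FVC and questionnaires, and the SAP window counts them as week 12.
- **Exposure is not confined to one arm.** Several triggers in 3.3.4.1 can apply to controls: treatments that interfere with nintedanib, other medical reasons, and non-compliance with trial procedures. Rehabilitation also runs only for the first 12 weeks.
- **Missing data were addressed.** The protocol planned a mixed model for week 24 and multiple imputation for the primary endpoint.

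All four points limit the finding, but they do not remove it. The consultation with the clinical monitor is case by case, covers adverse events only and schedules no visits. The window gives a mistimed value, not a week-12 one. Rehabilitation is the only assigned trial treatment, so that arm has an additional reason to stop. Neither planned method can draw on outcomes observed after stopping if none are scheduled, and the SAP no longer carries either analysis.

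**Conclusion.** The point holds as a gap between stated intention and scheduled visits. The protocol calls for data after treatment withdrawal but specifies no on-schedule Visit 5 or Visit 7 for a patient who stops and has not withdrawn consent. For stops before Visit 5, the week-12 6MWD is missing or mistimed. Week 24 is missing whenever the last visit is on or before day 126.

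The 3 to 14 m range applies only where values are missing, and rests on assumed stopping rates of 10% to 20%, assumed gaps of 30 to 70 m and uninformative loss in controls. No size or direction can be given where an early walk is used as week 12. Greater exposure of the rehabilitation arm is likely but not shown.

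With the SAP now descriptive only, no hypothesis test is affected. What remains is how far the observed-case summaries can be read as a comparison of the randomised groups.

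**What to change.** Reconcile Protocol 3.3.4, 3.3.4.1, 3.3.4.2, 6.1, 6.2.3 and the Flow Chart so that they say the same thing:

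- A patient who stops trial treatment but does not withdraw consent attends Visits 5 and 7 on the original schedule for the outcome assessments (6MWT, questionnaires, FVC, activity) and is analysed in the randomised arm.
- The early Visit 7 is reserved for patients who leave the trial.
- In SAP 6.7, an early-termination value does not stand in for a scheduled week-12 value. Changing the window alone would not be enough, because it turns a mistimed value into a missing one.

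This concerns data collection only and leaves decisions about stopping treatment untouched. As a change to the plan it is cheap, because the visits and procedures already exist. Some stoppers will decline, and the estimated effect may become slightly smaller. For the terminated trial, visits cannot be added afterwards; the descriptive report can still give, by arm, how many patients stopped early and how many week-12 values come from an early Visit 7.

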7. STATISTICAL METHODS AND DETERMINATION OF SAMPLE SIZE

7.1 STATISTICAL DESIGN - MODEL

This is a multi-centre, prospective, randomised, open label clinical trial to investigate the effect of pulmonary rehabilitation in patients with IPF currently **treated with** nintedanib at a dose of 150 mg bid for **up to 30** months.

The primary endpoint is the change from baseline in 6MWD at 12 weeks. 6MWD will be analysed on the original scale using the Analysis of Covariance (ANCOVA) model including intervention as a fixed categorical covariate and baseline 6MWD as a continuous covariate. More detail is provided in [Section 7.3.1](#).

The secondary and further endpoints are listed in [Section 5.1.1](#). The 12-week endpoints will be analysed using similar ANCOVA methodology as the primary endpoint. The 24-week endpoints will be analyzed using a mixed model with repeated measures. More detail is provided in [Section 7.3.2](#).

7.2 NULL AND ALTERNATIVE HYPOTHESES

The objective of this study is to demonstrate the difference of Nintedanib and pulmonary rehabilitation combination intervention compared to Nintedanib-only in the treatment of patients with IPF. This will be tested using the set of hypotheses indicated below. The null hypothesis is

H₀: No difference in mean for change in 6MWD at 12 weeks between Nintedanib and pulmonary rehabilitation combination intervention and Nintedanib-only intervention.

The alternative hypothesis is

H_a: The mean for change in 6MWD at 12 weeks is different for patients taking Nintedanib and pulmonary rehabilitation combination intervention than in Nintedanib-only intervention.

H₀ will be tested at the 5% level (two-sided test).

7.3 PLANNED ANALYSES

All individual data will be listed. Standard statistical parameters (number of non-missing values, mean, geometric mean, standard deviation (SD), median, quartiles, minimum and maximum) or frequency tables will be calculated where appropriate. In general, these parameters or frequencies will be calculated separately for each intervention, but jointly for all study centres.

The statistical analysis will be based on the following populations:

Randomized Set (RS): The Randomised set (RS) consists of those patients who were randomized to an intervention.

The efficacy will be conducted on the Randomized Set. For efficacy analysis, all measurements performed within visits 2-7 will be used.

Although there is no per protocol data set in the study, reasons for important protocol violations will be specified in the Trial Statistical Analysis Plan (TSAP). Patients with potential important protocol violations (those that relate to patient safety or efficacy) will be identified at Blinded Review Planning Meetings and listed in the clinical trial.

7.3.1 Primary endpoint analyses

The primary analysis is a restricted maximum likelihood (REML) based analysis of covariance (ANCOVA) comparing the change from baseline of 6MWD after 12 weeks of treatment with adjustment for the covariates of intervention as a fixed categorical covariate and baseline 6MWD value as a continuous covariate.

The statistical model will be as follows:

$$y_{ij} = \beta S_i + \tau_j + e_i$$

y_{ij} = response variable for the subject i receiving intervention j

β = fixed effect regression coefficient of baseline effect

S_i = the baseline measurement of subject i , $i = 1, 2, \dots$ where the baseline measurement is collected on Day 1 of the interventional period

τ_j = the fixed effect of intervention j , $j = 1, 2$

e_i = the random error associated with the i^{th} subject, identically independent normally distributed with mean 0 and unknown variance σ^2 .

The Kenward-Roger approximation will be used to estimate denominator degrees of freedom and adjust standard errors. Significance tests will be based on least-squares means using a two-sided $\alpha = 0.05$ (two-sided 95% confidence intervals). The primary intervention comparison will be the least-squares means contrast between interventions. Primary endpoint analyses will be done on complete cases. Section 7.3.2 discusses planned sensitivity analysis to assess the impact of patients missing post-randomisation data.

7.3.2 Secondary endpoint analyses

The secondary endpoints include those listed in [Section 5.1.1.2](#). All other secondary endpoints will be analysed on the original scales.

The 12-week secondary endpoints will be analysed equivalently as the primary endpoint using the ANCOVA model including intervention as a fixed categorical covariate and baseline value as a continuous covariate.

The 24-week secondary endpoints will be analysed with a restricted maximum likelihood (REML) based approach using a mixed model with repeated measurements (MMRM) comparing the change from baseline after 24 weeks of intervention. The analysis will include the fixed, categorical effects of intervention and the fixed continuous effects of baseline at each visit. Visit will be treated as the repeated measure with an unstructured covariance structure used to model the within-patient measurements. The statistical model will be as follows:

[figure not shown]
$$y_{ijk} = \beta_j S_i + \tau_{jk} + e_{ij}$$

$$e_{ij} \sim N_z(\mathbf{0}, \Sigma)$$

- y_{ijk} = response variable for the subject i at visit j receiving intervention k ,
- β_j = coefficient of baseline effect at visit j ,
- S_i = the baseline measurement of subject i , $i = 1, 2, \dots$
- τ_{jk} = the effect of intervention k at visit j ; $j = 1, 2, (3)$ and $k = 1, 2$
- e_{ij} = the random error associated with the j^{th} visit of the i^{th} subject, Errors are independent between subjects,
- Σ = an unstructured covariance matrix.

The Kenward-Roger approximation will be used to estimate denominator degrees of freedom and adjust standard errors. Significance tests will be based on least-squares means using a two-sided $\alpha = 0.05$ (two-sided 95% confidence intervals). The primary intervention comparison will be the least-squares means contrast between treatments.

A sensitivity analysis of the primary analysis will be performed using multiple imputation to handle missing data. All variables included in the analysis model will be included in the imputation model. In addition, after exploring the missing data mechanism and observed measurements on the blinded data, additional variables may be included in the imputation model, based on their associations with the observed endpoint value and/or the missingness mechanism. Those variables will be identified in the TSAP. For each imputed complete dataset, the primary analysis model will be used for the analysis. The results will be pooled following the standard multiple imputation procedure.

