7.7 DETERMINATION OF SAMPLE SIZE

In the 1199.187 6-month data, an unadjusted mean for absolute change from baseline in 6MWT distance of 4.9 meters (sd = 76.5) was observed for nintedanib. To conservatively estimate the sample size, a standard deviation of 85.0 is used in estimation. In the 2014 Cochrane Database of Systematic Reviews [[R18-1704](#)], a mean for absolute change from baseline in 6MWT distance of 44.3 meters was observed for pulmonary rehabilitation for interstitial lung disease. The minimal clinically important difference for the 6MWD for IPF patients with combined treatment of nintedanib and pulmonary rehabilitation versus IPF patients treated with nintedanib only is 30 meters [[R18-1767](#)].

In light of the available evidence, at least 254 patients would be required to provide 80% power to detect a difference in means of 30 meters between nintedanib and pulmonary rehabilitation combination treatment versus nintedanib by itself with a two-sided type-I error of 0.05. Assuming 10% drop out, at least 141 patients per arm, or 282 patients will be required. Calculations were performed using nQuery Advisor® 6.1 statistical package by Statistical Solutions Ltd. under the fixed term test of means with two groups option for student t-test with equal variance.

Difference in Means	Common Standard Deviation	Power (%)	Total N of randomized patients
30.0	77.0	80	210
30.0	85.0	80	254

8. INFORMED CONSENT, TRIAL RECORDS, DATA PROTECTION, PUBLICATION POLICY, AND ADMINISTRATIVE STRUCTURE

The trial will be carried out in compliance with the protocol, the ethical principles laid down in the Declaration of Helsinki, in accordance with the ICH Harmonized Tripartite Guideline for Good Clinical Practice (GCP), relevant BI Standard Operating Procedures (SOPs),

Standard medical care (prophylactic, diagnostic and therapeutic procedures) remains the responsibility of the treating physician of the patient.

The investigator will inform the sponsor immediately of any urgent safety measures taken to protect the trial patients against any immediate hazard, as well as of any serious breaches of the protocol or of ICH GCP.

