7.4.2 Sensitivity analysis of the primary endpoint

~~Multiple imputation will be used to handle missing data as a sensitivity analysis using the RS set. All variables included in the analysis model will be included in the imputation model. In addition, after exploring the missing data mechanism and observed measurements on the blinded data additional variables may be included in the imputation model.~~

~~When there is no missing baseline information in the imputation model, regression method will be used. When there is missing baseline information in the imputation model, MCMC method will be used. For each imputed complete dataset, the primary analysis model will be~~

used for the analysis. The results will be pooled following the standard multiple imputation procedure.

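### The minimum imputation the protocol commits to repeats the complete-case estimate, so it does not assess the impact of missing 12-week walks

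*Protocol*

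**What the plan says.** Protocol 7.3.1 fits an ANCOVA with arm and baseline 6MWD to patients who have a week-12 walk. It gives the purpose of the missing-data check: "Section 7.3.2 discusses planned sensitivity analysis to assess the impact of patients missing post-randomisation data".

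Protocol 7.3.2 describes that check as multiple imputation (MI). Its compulsory content is "All variables included in the analysis model will be included in the imputation model". Other variables may be added after a blinded look at the data, if they relate to the endpoint or to missingness, and the SAP is to name them. Each completed dataset is analysed with the primary model and the results are pooled. Protocol 7.5 leaves the detail to the SAP.

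SAP 7.4.2 carried the method over ("Multiple imputation will be used to handle missing data as a sensitivity analysis using the RS set"), kept further variables optional, named none in the visible text, and added only the choice between regression and MCMC. That text is now struck through. SAP Section 4 limits the primary and secondary endpoints to descriptive measures after the trial's termination, SAP 7.4.1 follows suit, and SAP 6.6 uses observed cases. Neither document plans a delta-adjusted, reference-based or tipping-point analysis.

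**The concern.** A sensitivity analysis should change the assumption whose effect is in doubt. Here the doubtful assumption is that a rehabilitation patient without a week-12 walk did as well as similar rehabilitation patients who walked. The complete-case ANCOVA makes that assumption given arm and baseline, and an MI built on arm and baseline makes it again.

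Selective loss in one arm is plausible: allocation is open (Protocol 4.1.5.1), and rehabilitation stops when a patient is judged no longer suitable for it (Protocol 1.4). If the minimum version were run, close agreement between the two estimates could be read as robustness although nothing had been tested.

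**Working it through.** **1. The plan's own figures.** Protocol 7.7 states "at least 254 patients would be required to provide 80% power to detect a difference in means of 30 meters", and "a standard deviation of 85.0 is used in estimation", with a two-sided 5% test. Per arm:

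n = 2(z₀.₉₇₅ + z₀.₈₀)²σ²/Δ² = 2(1.960 + 0.842)² × 85²/30² = 126.02, rounded up to 127, or 254 in total.

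The exact two-sample t calculation also gives 254 (power 80.0%). For dropout the protocol says "Assuming 10% drop out, at least 141 patients per arm, or 282 patients will be required": 127/0.9 = 141.1. Rounding up would give 142, but this is immaterial because 145 per arm are planned and 145 × 0.9 = 130.5 exceeds 127.

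**2. Why the minimum MI adds nothing.** Let X hold the intercept, arm and baseline, with rows split into observed (o) and missing (m) outcomes, and let b be the complete-case estimate.

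- Complete case: Xo′yo = Xo′Xo b.
- Imputed outcomes average Xm b over the imputations.
- Refit on all rows: (X′X)⁻¹(Xo′Xo b + Xm′Xm b) = (X′X)⁻¹(X′X) b = b.

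MI therefore converges to the complete-case estimate, whatever caused the missingness. This needs the baseline to be present. SAP 6.7 replaces a missing baseline by the screening value where there is one, so outcome-only missingness is the realistic case.

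**3. Simulation of the minimum version.** 290 patients allocated 1:1, true difference 30 m, residual SD 85, 1,000 trials per scenario, 50 imputations. Assumed, not in the documents: baseline SD 100 m, an auxiliary variable correlated 0.6 with the outcome, and missingness models giving 8.5% to 11.5% missing overall.

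| Missingness | Complete case (m) | MI, arm + baseline (m) |
|---|---|---|
| Completely at random | 30.17 (SE 10.52) | 30.19 (SE 10.54) |
| Depends on baseline | 29.66 | 29.68 |
| Depends on the auxiliary, PR arm | 35.92 | 35.93 |
| Depends on the unseen walk, PR arm | 37.99 | 37.99 |

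The mean difference is at most 0.02 m. Its trial-to-trial SD is 0.4 to 0.5 m with 50 imputations and 0.06 m with 2,000, so it is Monte Carlo noise. In the last two rows MI repeats a bias of about 6 to 8 m in full.

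**4. With the auxiliary in the imputation model** (fresh simulated trials). Where missingness depends on the auxiliary: complete case 35.8 m, MI 30.1 m. Where it depends on the unseen walk: complete case 38.5 m, MI 35.7 m, so only part of the bias goes.

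**5. Size at the protocol's dropout.** Assume PR patients with a missing walk gain nothing and the others gain 30 m. The all-patient difference is 0.90 × 30 + 0.10 × 0 = 27 m. A separate simulation (1,500 trials, 20 imputations, 10% missing per arm) gave 29.9 m for both complete case and MI. The overstatement is about 30 − 27 = 3 m, against a standard error of 85 × √(2/130.5) = 10.5 m.

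If a fraction f of those no-benefit patients has an early-termination walk counted at week 12, the overstatement is 27/(1 − 0.10(1 − f)) − 27. That is 3.0 m at f = 0, 1.4 m at f = 0.5 and 0 at f = 1. The documents give no value for f.

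**6. What a delta analysis does.** Lowering imputed PR-arm walks by δ shifts the estimate by about −δ × (missing share in the PR arm). At 10% missing, δ = 0, 10, 20 and 30 m give 0, −1, −2 and −3 m. Simulated shifts for δ = 15, 30 and 60 m were −1.5, −2.9 and −6.0 m, in line with the formula.

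**The case against.** Several stronger readings are tempting, and the documents do not support them.

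- **That the MI can never show the effect of missing data.** Protocol 7.3.2 allows variables chosen for their link to the endpoint or to missingness, and step 4 shows that an informative one can move the estimate by 5.7 m. The identity in step 2 holds for the permitted minimum only. That no variable is named also rests on the visible text: the SAP's contents list passes from Section 8 to Section 10.
- **That stopping rehabilitation means a missing walk.** Protocol 3.3.4 asks that randomised patients be kept in the trial or at least followed for important data. Protocol 5.1.2.1 keeps patients who cannot complete the test. Protocol 6.1 and 6.2.3 ask for Visit 7 procedures, including the walk, at early termination. SAP 6.7 allocates walks on days 2 to 126 to week 12. Many who stop could be observed.
- **That the MI conflicts with a rule to use all data regardless of adherence.** Protocol 7.3 says "For efficacy analysis, all measurements performed within visits 2-7 will be used", which does not mention adherence. The independence statement in SAP 6.1 concerns nintedanib, not rehabilitation attendance.
- **That the bias would be 6 to 9 m, and that control-based imputation is shown to be right.** Those sizes need 20% to 30% loss in the PR arm under zero benefit, and the protocol's only dropout figure is 10%. Control-based imputation recovers the truth in such a simulation because both assume that dropouts do no better than controls.
- **That the report will carry a false claim of robustness.** The final SAP strikes the MI and the ANCOVA, so neither will be run.

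These objections limit the size and urgency of the point. They leave the gap in the plan: optional auxiliary variables, none named, and no analysis that departs from missing at random.

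**Conclusion.** The concern holds for what the protocol commits to. The compulsory imputation model contains the same variables as the complete-case ANCOVA and feeds the same model, so it returns the same estimate up to Monte Carlo noise and does not serve the purpose that 7.3.1 gives it. This rests on missingness confined to the outcome and on imputation and analysis models of the same form. Adding informative variables would help where missingness follows them, but untested departures from missing at random would remain.

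The likely size is modest: about 3 m of 30 m at 10% dropout, under the illustrative zero-benefit assumption, falling towards zero as early-termination walks are obtained. That is below a third of the standard error. Because the trial was terminated and the SAP is now descriptive, the point matters for any between-arm difference that is reported. The observed-case summaries face the same selective loss without a check.

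**What to change.** In Protocol 7.3.2 and 7.5, for any inferential comparison:

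- Keep the MI, but make informative variables already collected compulsory and name them: for example the week-24 walk, baseline and follow-up FVC and DLco, and rehabilitation attendance within the PR arm. Some of these will be missing too, so the imputation method must allow for that. Patients who leave before week 12 have few of them, which is why the next item is needed.
- Add a delta-adjusted analysis that lowers imputed PR-arm week-12 walks by 0, 10, 20 and 30 m. Control-based imputation can be an optional further scenario.

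For the abbreviated report under the final SAP, put these results beside any between-arm difference in 6MWD. If none is reported, show the number of missing week-12 walks by arm beside the observed-case summaries.

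The cost is a little extra analysis on data already collected, and a sensitivity estimate that may look less favourable.
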